- 238 interview. This will determine the subjective vividness, valence, and encapsulated beliefs' strength
- associated with the index trauma memory (Hackmann et al., 2000). The same trauma memory will be
- 240 used for repeated assessments of its subjective vividness, valence, and encapsulated belief(s).
- 241 Previous treatments, and whether or not they were PTSD-focused and of what type, will be recorded
- at baseline.

244 **6.4.2 Study Assessment Moments**

245 Outcome instruments will be assessed before naturalistic wait, at baseline (just before treatment

- starts), after 6 sessions (3-4 weeks of treatment), after another 6 sessions (another 3-4 weeks) at
 post-test, 8 weeks after the last session, and at a one-year follow-up (one year after baseline just
- 248 before treatment starts).
- 249

250 **6.4.3** Assessment Procedures

251 An independent research assistant at the site who is blind for the patients' treatment condition will 252 take the interviews and have the participant fill out the self-report instruments at a PC. Each 253 assessment will take 3 hours at max. Patients and therapists will not be informed about the results of 254 assessments, until the evaluation after the assessment 8-weeks after treatment completion. To 255 assess treatment integrity, all sessions will be video recorded and per participant a random sample of 256 the first 6 sessions and a random sample of the last 6 sessions will be drawn to be rated by 257 independent trained judges for treatment adherence, blind for condition. The videos will also be 258 used to study other issues that might be raised during the study, e.g. the therapeutic alliance, and 259 exploration of immediate effects of specific micro-techniques. Recordings will be destroyed 5 years 260 after publication of the main findings.

261

262 **7. Statistical analysis**

Mixed regression analysis taking all available data into account will be used to analyse the data. For
 diagnostic outcome mixed logistic regression analysis will be used, for skewed distributions mixed
 gamma regression, for medication use Poisson or negative binomial regression.

266

267 8. Adjacent studies

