268 8.1 Specificity of memories. An adjacent study aims to test whether memories of single trauma are 269 more specific and consistent than those of repeated traumas. Participants are asked to write an 270 account of the index trauma and where there are multiple traumas that constitute the index trauma, 271 to describe the one they have the clearest memory of, at baseline and again at follow-up. The 272 complete task will take about 30 minutes. The (anonymized) reports will be coded by independent 273 raters blind for whether the trauma is single or repeated. Narratives will also be coded for use of 274 event-specific and generic information, on coherence, and on use of conceptual and sensory words 275 by dividing them into utterance units, defined as clauses with a single thought, idea or action (see 276 Jones et al., 2007). This adjacent study is done under direction of and in collaboration with [name] 277 [name], Royal Holloway University, UK. An additional issue that will be explored is to what degree

- 278 memory accounts are influenced by treatment, and whether the two treatments differ in this
- 279 respect. See appendix 1 for further information.
- 280 8.2 Qualitative study into patients' perspectives. A second adjacent study will focus on the 281 perspectives of patients on both treatments. Two topics will be explored in this qualitative study: 282 topic one will look at the process of change and treatment engagement and processes; topic two will 283 explore effective elements of the specific treatments, the relationship between these effective 284 elements on PTSD symptom severity, and the differences between the two treatments. This will be 285 done in a subsample of the study population, N=20 from Perth, and N=20 from the Dutch sites, with 286 equal proportions from both arms. The appendix 2 describes the overall study in detail. 287 8.3 Change in schema modes as an index of personality problems. A third adjacent study will assess 288 how schema modes change along the treatments, as an index of change in personality problems that 289 are common in PTSD related to childhood trauma. Appendix 3 provides more information.

8.4 Essential ingredients of ImRs: an observational study. This study will use video recordings of
 ImRs sessions to explore on a microscopic observational level what specific ingredients of ImRs are
 associated with change, with a specific focus on two possible processes: expression of inhibited

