- 852 The last years there has been done a lot of research of the underlying mechanisms of ImRs. One 853 explanation of ImRs is that it helps the patient to express inhibited action tendencies and get unmet 854 needs met (Arntz, 2012).
- 855

856 Hypothesis: As more inhibited action tendencies are being expressed and unmet needs of safety are 857 met, the PTSD symptoms will decrease in patients with early childhood trauma.

858

859 860 2. Aim

861 To clarify the working mechanisms of the ImRs protocol, in order to enlarge the chance of a 862 successful treatment of PTSD-symptoms with clients with early childhood trauma.

863 864 3. Study design

865 The study is a multi-centre Randomized Clinical Trial (RCT). There are five or six assessments: at start 866 of wait (if applicable), just before treatment, halfway treatment, after treatment, 8 weeks after 867 treatment, and at 1-year follow-up. At participating sites there usually is a naturalistic wait of 868 approximately 6 weeks (estimated mean). To assess changes due to time only, assessments take 869 place before and after wait. In case there is no naturalistic wait before treatment can start, the pre-870 wait assessment will be skipped.

- 871 At start of every session a self-report of PTSD symptoms will be taken to explore whether treatments 872 differ in their speed of improvement in the three symptom clusters of PTSD.
- 873 874 Substudy
- 875 All sessions will be audio recorded. Recordings will be destroyed 5 years after publication of the main 876 findings. Non-drawn recordings will be destroyed immediately.
- 877

- 878 The records of ImRs will be rated by 2 independent trained judges on: 879
 - 1. The expression of inhibited action tendencies
 - 2. Get unmet needs met.
- 881 882 Uitwerking
- 883 What are inhibited action tendencies?
- 884 885 Emotion Action tendency 886 Helplessness, fear Attack the other and defend oneself

887 888	Helplessness, anger	Attack the other, to put the other in his place, to destroy the other.	
889	What are the unmet needs	2	
890	what are the uniner needs		
801	Emotion	Needs	
802	Elliotion Helplessness fear	Neeus Safaty comfort to everyon and's feelings, recognition	
092 902		Becognition to express one's feelings, recognition	
093	Reipiessness, anger	Recognition, to express one's reelings, safety	
094	Grieve	Safety, comfort, to express one's reelings, recognition	
893	Guilt	Reassurance, reattribution, blaming the correct person	
890	Sname	idem.	
89/			

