898	Instruments		
899	- IES-R (Self-reported PTSD-symptoms)		
900	- Caps		
901			
902	4. Study population		
903			
904	4.1 population		
905	Adult patients with a prima	rry diagnosis of PTSD due to trauma(s) that took place before the age of 16	
906	and participate in the IREN	trial.	
907			
908	4.2 Inclusion criteria		
909	See RCT study protocol		
910			
911	4.3 Exclusion criteria		
912	See RCT study protocol.		
913			
914	4.4 Sample size calculation		
915	Will be based on a power a	nalysis not yet completed.	
916			
917	5. treatment		
918			
919	5.1 Investigational treatme	ent	
920	See RCT study protocol.		
921			
922	5.2 Use of co-intervention		
923	See RCT study protocol.		
924			
925	5.3 Escape medication/tre	atment	
926	See RCT study protocol.		
927			
928	5.4 Further treatment		
929	See RCT study protocol.		
930			
931	6. Outcome		
932			
933	6.1 Main study parameter	/endpoint	
934	This will be a qualitative stu	udy using MAXQDA, a computer program for qualitative data analysis.	
935		, , , , , , , , , , , , , , , , , , , ,	
936	6.2 Secondary study paran	neters	
937	N.A.		
938			
939	6.3 Randomisation, blindir	ng and treatment allocation	

- 940 See RCT study protocol
- 941

942 **6.4 Study procedures**

943 See RCT study protocol.944

945 **7. Statistical analysis**

946 This will be a qualitative study using MAXQDA, a computer program for qualitative data analysis. 947

948 8. Adjacent study

949 N.A.

950

951 **9.** Dissemination and Implementation.

- 952 The results of this substudy will be processed in a scientific article.
- 953 Presentations to enlarge the expertise of the participating therapists and other clinicians. Findings
- 954 will be used to adapt existing ImRs treatment protocols.
- 955

956 **10. Time schedule**

957 See RCT study protocol. 958

959 **11. References**

- 960 Arntz, A. (2012). Imagery rescripting as a therapeutic technique; Review of clinical trials, basic
- 961 studies, and research agenda. *Journal of Experimental Psychopathology*. 3, 189-208.

- 964 Oxford, UK: Oxford University Press.
- 965

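### Appendix 4 contradicts the main protocol on recording medium and retention, and its qualitative-only analysis does not test its own graded hypothesis

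*Protocol*

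**What the plan says.** **Recordings, main protocol.** Section 6.4.3 states that "all sessions will be video recorded and per participant a random sample of" the first six sessions, and another of the last six, is drawn for adherence rating. The size of these samples is not given. The videos will also be "used to study other issues that might be raised during the study, e.g. the therapeutic alliance, and" the immediate effects of micro-techniques. Recordings are destroyed five years after publication of the main findings, with no separate rule for undrawn sessions. Section 8.4 introduces this substudy with "This study will use video recordings of" ImRs sessions and asks which ingredients are associated with change.

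**Recordings, Appendix 4.** Section 3 (Substudy) states: "All sessions will be audio recorded". It repeats the five-year rule and then adds "Non-drawn recordings will be destroyed immediately". It describes no draw of its own. For study procedures, its section 6.4 refers back to the main protocol.

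**Hypothesis and analysis, Appendix 4.** The hypothesis reads "As more inhibited action tendencies are being expressed and unmet needs of safety are" met, PTSD symptoms will go down. Two independent judges rate the ImRs records on both features. IES-R and CAPS are the listed instruments. Section 4.4 leaves the sample size to a power analysis not yet done. Sections 6.1 and 7 both say only: "This will be a qualitative study using MAXQDA, a computer program for qualitative data analysis".

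**The concern.** There are two separate problems.

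The first is a contradiction with an irreversible consequence. A site that follows Appendix 4 discards recordings that a site following 6.4.3 keeps. The only draw described anywhere is the one in 6.4.3, made to check treatment integrity. On a literal reading, that draw decides which sessions survive for mechanism work, a purpose it was not designed for.

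The second is a mismatch of hypothesis and analysis. A statement that more of one thing goes with less of another needs an estimate of association. The appendix plans the inputs for one (ratings, symptom scores, a power analysis) and then names an analysis that does not produce it. This is not detail left to a later analysis plan, because the appendix's own statistical section fixes the method.

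Testing working mechanisms is the secondary aim of the trial (section 2), and section 9 of Appendix 4 says the findings will be used to adapt ImRs treatment protocols. The conclusion should therefore rest on an analysis that can support it.

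**Working it through.** Appendix 4 gives no sample size, power or alpha, so it has no figure to reproduce. The check compares the texts and then sizes the possible loss.

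**1. Texts side by side**

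| Item | 6.4.3 | 8.4 | Appendix 4 |
|---|---|---|---|
| Medium | video | video | audio |
| Drawn recordings | kept to 5 years after publication | not stated | kept to 5 years after publication |
| Undrawn recordings | same rule, no exception | not stated | destroyed at once |
| Purpose of draw | adherence rating | not stated | not stated |
| Number drawn | not stated | not stated | not stated |

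Medium and retention of undrawn recordings conflict. Retention of drawn recordings does not.

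**2. Share of recordings lost**

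Inputs: 12 sessions per patient (the maximum in section 5.1; early completion is allowed); k sessions drawn per half (assumed); 142 / 2 = 71 ImRs patients (N from section 4.4, balanced arms assumed). Full volume is 71 × 12 = 852 recordings. Share destroyed = 1 − 2k/12.

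| k per half | Kept (71 × 2k) | Destroyed |
|---|---|---|
| 1 | 142 | 1 − 2/12 = 83% |
| 2 | 284 | 1 − 4/12 = 67% |
| 3 | 426 | 1 − 6/12 = 50% |
| 6 | 852 | 0% |

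**3. What the loss does to a session-level analysis**

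Suppose the rating in session t is to predict the next IES-R, given IES-R at the start of session t. This needs a recording of session t only. Section 6.2 collects IES-R at the start of every session and at every assessment, whether or not the recording is drawn, and the post-test score serves after session 12. Consecutive recordings are not required.

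The cost is precision. As a rough guide, if rated sessions contributed independent information, the standard error would grow by √(852/kept):

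- k = 1: √6 = 2.4
- k = 2: √3 = 1.7
- k = 3: √2 = 1.4

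**4. Could the retained material still bear on the hypothesis?**

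With one mean rating per patient and 71 patients, the correlation detectable with 80% power at two-sided 0.05 (Fisher z) is tanh[(1.960 + 0.842)/√(71 − 3)] = tanh(0.340) = 0.33, with no dropout. So it could. A patient-level correlation is, however, the weaker design. Section 6.2 lets therapists use the IES-R ratings to steer treatment, so current symptoms may shape session content. Adjusting for IES-R at session t addresses this; a patient-level correlation does not.

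**5. Hypothesis against analysis**

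The hypothesis is graded and directional, and its inputs are numerical. Sections 6.1 and 7 name no estimate relating ratings to IES-R or CAPS, and a power analysis has no test to refer to. The analysis as written does not test the hypothesis.

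**The case against.** The strongest reply is that this is an exploratory adjacent study and little is really lost. Drawn recordings are kept, and adherence rating needs only those. Appendix 4 never says it needs every session, and if its own draw took all ImRs sessions, none of those recordings would be lost. The later uses in 6.4.3 are open-ended. The ratings and symptom scores are planned, so a quantitative model can be added at any time. Rating every session would be heavy: 2 judges × 852 sessions × 1.5 hours = 2,556 hours. Longer storage of trauma-therapy video is not neutral for participants either.

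Much of this stands. A reader might infer that Appendix 4 destroys the recordings it needs and that its question therefore cannot be answered. The documents do not support that: drawn sessions survive, the inputs for a quantitative test are planned, and the model above runs on drawn sessions alone. The 83% figure is likewise not the protocol's; it holds only if one session per half is drawn.

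The reply does not remove the contradiction on medium and retention, and it does not make a qualitative analysis test a graded hypothesis. Nor can an undrawn session be recovered once destroyed, if one of the uses named in 6.4.3 is later taken up.

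**Conclusion.** The point holds in two limited parts.

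- **Recordings.** Appendix 4 conflicts with 6.4.3 and 8.4 on medium, and with 6.4.3 on retention of undrawn recordings. Followed as written, it permanently removes material reserved for alliance and micro-technique work and reduces the sessions open to mechanism analysis. The loss is 83% to 50% of recordings if one to three sessions per half are drawn, assuming full 12-session courses. The true share depends on a draw that the protocol does not state. The consequence is lower precision and forgone later uses; the substudy question remains answerable.
- **Analysis.** The hypothesis in Appendix 4 is not tested by the analysis in its sections 6.1 and 7, and the announced power analysis does not fit a qualitative method.

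The primary CAPS comparison, the main sample size and the main analysis are not affected. The change is still worth making because destruction is irreversible and the correction is cheap.

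**What to change.** 1. Before any recording is destroyed, reconcile section 6.4.3, section 8.4 and Appendix 4 section 3 on medium and retention. Use one rule that matches the consent text. That text was not available for this check, so the destruction sentence should not simply be deleted.
2. State in Appendix 4 which ImRs sessions are drawn for rating, how many per patient, and whether this is the adherence draw of 6.4.3 or a separate one.
3. In Appendix 4 section 7 (and 6.1 to match), choose one of two routes:
   - Add a mixed regression on the rated sessions, with repeated sessions nested in patients. The judges' rating in session t predicts IES-R at the next measurement, adjusted for IES-R at the start of session t and for session number. Base the power analysis on this model and keep MAXQDA for description.
   - Restate the hypothesis as a qualitative question and drop the power analysis.

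**Cost.** Appendix wording, some analysis time, and storage if the longer retention rule is the one consented to. Rating all sessions is not required. With one session per half, rating takes 2 × 142 × 1.5 = 426 hours instead of 2,556. The price of rating only drawn sessions is the loss of precision shown above.
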